9.2.8 Immune-mediated Adverse Events

Immune-mediated AEs are AEs consistent with an immune-mediated mechanism or immune-mediated component for which non-inflammatory etiologies (eg, infection or tumor progression) have been ruled out. Immune-mediated AEs can include events with an alternate etiology, which were exacerbated by the induction of autoimmunity. Information supporting the assessment will be collected on the participant's CRF.

9.2.9 Other Safety Considerations

Any significant worsening noted during interim or final PEs, ECG, x-ray filming, any other potential safety assessment required or not required by protocol should also be recorded as a nonserious or serious AE, as appropriate, and reported accordingly.

9.3 Overdose

An overdose is defined as the accidental or intentional administration of any dose of a product that is considered both excessive and medically important. Overdoses that meet the regulatory definition of SAE will be reported as an SAE (see Appendix 3).

For this study, any dose of study drug greater than the assigned dose and considered excessive and medically important by the Investigator will be considered an overdose.

In the event of an overdose, the Investigator should:

1) Contact the Medical Monitor immediately.

Protocol Amendment No.: 07

2) Closely monitor the participant for AEs/SAEs and laboratory abnormalities until BMS-986258 can no longer be detected systemically.

- 3) Obtain a serum sample for PK if requested by the Medical Monitor (determined on a case-by-case basis).
- 4) Document the quantity of the excess dose as well as the duration of the overdosing in the CRF.

Decisions regarding dose interruptions or modifications secondary to an overdose will be made by the Investigator in consultation with the Medical Monitor based on the clinical evaluation of the participant.

9.4 Safety

Planned time points for all safety assessments are listed in the Schedule of Activities

9.4.2 Clinical Safety Laboratory Assessments

- Investigators must document their review of each laboratory safety report.
- A local laboratory will perform the analyses and will provide reference ranges for these tests. Results of clinical laboratory tests performed on Day -1 must be available prior to dosing.
- The laboratory tests that will be performed for study participants are shown in Table 9.4.2-1.
- Results of all laboratory tests required by this protocol must be provided to the Sponsor, recorded either on the laboratory pages of the CRF or by another mechanism as agreed upon between the Investigator and BMS (eg, provided electronically). If the units of a test result differ from those printed on the CRF, the recorded laboratory values must specify the correct units. Any abnormal laboratory test result considered clinically significant by the Investigator must be recorded on the appropriate AE page of the CRF.

Table 9.4.2-1: Clinical Laboratory Assessments
Hematology
Hemoglobin and hematocrit
Total leukocyte count, including differential
Platelet count
Prothrombin time, activated partial thromboplastin time, and international normalized ratio (at screening only)
Coagulation (screening only)

Protocol Amendment No.: 07

Table 9.4.2-1: Clinical Laboratory Assessments				
Serum Chemistry				
Aspartate aminotransferase Alanine aminotransferase Total bilirubin Direct bilirubin (reflex only) ^a Alkaline phosphatase Lactate dehydrogenase Creatinine Creatine kinase/ Creatine phosphokinase C-reactive protein Blood urea nitrogen or urea Uric acid Glucose Lipase Amylase	Total protein Albumin Sodium Potassium Chloride Calcium Phosphorus Magnesium Creatinine clearance (Cockcroft-Gault method) (screening only) Troponin			
Gamma glutamyl transferase (reflex only) ^b Thyroid stimulating hormone Free T3 and T4 (screening and reflex only) ^c				
Urinalysis				
Protein Glucose Blood				
Leukocyte esterase Specific gravity pH Microscopic examination of the sediment if blood, pro	otein or leukocytes esterase are positive on the dipstick			
Serology	· · · · · ·			
	HIV-1 and HIV-2 Ab (at screening, and as mandated by			
Other Analyses				
Pregnancy test (WOCBP only: screening, predose, dis FSH (screening only and women only)	scharge).			

^a Reflex testing to be performed only if total bilirubin is abnormal.

9.4.3 Imaging Safety Assessment

Any incidental findings of potential clinical relevance that are not directly associated with the objectives of the protocol should be evaluated and handled by the Study Investigator as per standard medical/clinical judgment.

Protocol Amendment No.: 07

b Reflex testing to be performed only if liver function test is abnormal.

^c Reflex testing to be performed only if TSH is abnormal.

9.4.4 Physical Examinations

Refer to the Schedule of Activities for timing of assessments

9.4.5 Vital Signs

Refer to the Schedule of Activities for timing of assessments

9.5 Pharmacokinetics

The PK of BMS-986258 and nivolumab will be derived, if feasible, from serum concentrations versus time data in monotherapy and in combination with nivolumab. The PK parameters that will be assessed following serial PK collection are shown in Table 9.5-1. Sparse nivolumab concentration-time data will be collected and may be used in an integrated PPK or ER analysis along with data from other nivolumab studies, which would be the subject of a separate report.

Individual participant PK parameter values will be derived by non-compartmental methods by a validated PK analysis program. Actual times will be used for the analyses.

Table 9.5-1: Pharmacokinetic Parameters

Abbreviation	Definition		
Parameters to be Reported Separately in Cycle 1 for Parts A, A1, and B			
Cmax	Maximum observed serum concentration		
Tmax	Time of maximum observed serum concentration		
AUC(0-T)	Area under the serum concentration-time curve from time zero to time of last quantifiable concentration		
Ctau	Concentration at the end of the dosing interval		
AUC(TAU)	Area under the concentration-time curve in one dosing interval		

Parameters that May Potentially be Assessed Following the Dose Administration in Cycle 3 for Parts A and B			
CLT	Total body clearance		
Css-avg	Average concentration over a dosing interval (AUC[TAU]/tau)		
AI_AUC	AUC accumulation index; ratio of AUC(TAU) at steady state to AUC(TAU) after the first dose		
T-HALFeff_AUC	Effective elimination half-life that explains the degree of accumulation observed		

Protocol Amendment No.: 07

Table 9.5-1: Pharmacokinetic Parameters

[figure not shown]

Table 9.5-2: Pharmacokinetic and Immunogenicity Sampling Schedule for BMS-986258 Q4W in Monotherapy Dose Escalation (Part A)

Study Day of Sample Collection (1 Cycle = 8 Weeks)	Event	Time (Relative to BMS- 986258 Dose) Hour:Min	PK Serum Samples for BMS-986258	ADA Samples for BMS-986258
Cycle 1 Day 1	Predose ^a	00:00	X	X
Cycle 1 Day 1	EOIb	EOI ^b	X	
Cycle 1 Day 1		04.00	X	
Cycle 1 Day 2		24:00	X	
Cycle 1 Day 3-Day 5		48:00-96:00	X	
Cycle 1 Day 8		168:00	X	
Cycle 1 Day 15		336:00	X	
Cycle 1 Day 22		504:00	X	
Cycle 1 Day 29	Predose ^a	00:00	X	X
Cycle 1 Day 29	EOIb	EOI ^b	X	
Cycle 2 Day 1	Predose ^a	00:00	X	X
Cycle 2 Day 29	Predose ^a	00:00	X	X

Protocol Amendment No.: 07

analysis of samples.

Table 9.5-2: Pharmacokinetic and Immunogenicity Sampling Schedule for BMS-986258 Q4W in Monotherapy Dose Escalation (Part A)

Study Day of Sample Collection (1 Cycle = 8 Weeks)	Event	Time (Relative to BMS- 986258 Dose) Hour:Min	PK Serum Samples for BMS-986258	ADA Samples for BMS-986258
Cycle 3 Day 1	Predose ^a	00:00	X	X
Cycle 3 Day 1	EOI ^b	EOIb	X	
Cycle 3 Day 1		04.00	X	
Cycle 3 Day 2		24:00	X	
Cycle 3 Day 3-Day 5		48:00-96:00	X	
Cycle 3 Day 8		168:00	X	
Cycle 3 Day 15		336:00	X	
Cycle 3 Day 22		504:00	X	
Cycle 3 Day 29	Predose ^a	00:00	X	X
Cycle 5 and every other cycle (i.e., cycle 7, 9,) Day 1	Predose ^a	00:00	X	X
EOT		00:00	X	X
30 day follow up			X	X
60 day follow up			X	X
100 day follow up			X	X

Abbreviations: ADA, anti-drug antibody; EOI, end of infusion; EOT, end of treatment; PK, pharmacokinetics.

^a Predose: All predose samples should be taken within 30 minutes prior to the start of any treatments.

b The EOI occurs when the entire BMS-986258 dose in the infusion bag is administered to the patient. If diluent is used to flush the dose remaining in the infusion line, then the EOI will occur when there is no dose is remaining in the infusion line after a flush. A PK sample should be taken immediately prior to the EOI (preferably within 2 minutes prior to the EOI). If the EOI is delayed to beyond the nominal infusion duration (30 minutes), the collection of this sample should also be delayed accordingly. EOI samples may not be collected from the same IV access as the drug was administered.

Clinical Protocol BMS-986258

Table 9.5-3: Pharmacokinetic and Immunogenicity Sampling Schedule for BMS-986258 Q4W in Subcutaneous PK Sub-study (Part A1)

CA031002

Anti-TIM-3 mAb

Study Day of Sample Collection (1 Cycle = 8 Weeks)	Event	Time (Relative to BMS-986258 Dose) Hour:Min	PK Serum Samples for BMS- 986258	ADA Samples for BMS- 986258	
		Subcutane	ous Administr	ation	
Cycle 1 Day 1	Predose ^b	00:00	X	X	
Cycle 1 Day 2		24:00	X		
Cycle 1 Day 4- Cycle 1 Day 5		72:00-96:00	X		
Cycle 1 Day 8		168:00	X		
Cycle 1 Day 15		336:00	X		
Cycle 1 Day 22		504:00	X		
		Intraveno	ous Administra	tion	
Cycle 1 Day 29	Predose ^b	00:00	X	X	
Cycle 1 Day 29	EOI ^c	EOI ^c	X		
Cycle 1 Day 31- Cycle 1 Day 33		48:00- 96:00	X		
Cycle 1 Day 36		168:00	X		
Cycle 1 Day 43		336:00	X		
Cycle 1 Day 50		504:00	X		
Cycle 2 Day 1	Predose ^a	00:00	X	X	
Cycle 2 Day 29	Predose ^a	00:00	X	X	
Cycle 3 Day 1	Predose ^a	00:00	X	X	
Cycle 3 Day 1	EOI ^c	EOI ^c	X		
Cycle 3 Day 29	Predose ^a	00:00	X	X	
Cycle 5 and every other cycle (i.e., cycle 7, 9,) Day 1	Predose ^a	00:00	X	X	
ЕОТ		00:00	X	X	
30 day follow up			X	X	
60 day follow up			X	X	
100 day follow up			X	X	

Protocol Amendment No.: 07

Date: 16-Jun-2021 108

Abbreviations: ADA, anti-drug antibody; EOI, end of infusion; EOT, end of treatment; IV, intravenous; PK, pharmacokinetics; Q4W, every 4 weeks.

Table 9.5-4: Pharmacokinetic and Immunogenicity Sampling Schedule for BMS-986258 Q4W in Combination with Nivolumab Q4W in Dose Escalation (Part B)

0.15.6		m.	DIZ C	il —		
Study Day of	Event	Time	PK Serum		ADA	
Sample		(Relative To	Samples for		Samples for	
Collection		BMS-986258	BMS-986258		BMS-	
(1 Cycle = 8		Dose)			986258	
Weeks)		Hour:Min				
Cycle 1 Day 1	Predose ^a	00:00	X		X	
Cycle 1 Day 1	EOI ^b	EOIb	X			
Cycle 1 Day 1		04.00	X			
Cycle 1 Day 2		24:00	X			
Cycle 1 Day 3-		48:00-96:00	X			
Day 5						
Cycle 1 Day 8		168:00	X			
Cycle 1 Day 15		336:00	X			
Cycle 1 Day 22		504:00	X			
Cycle 1 Day 29	Predose ^a	00:00	X		X	
Cycle 1 Day 29	EOIb	EOIb	X	*	X	
Cycle 2 Day 1	Predose ^a	00:00	X		X	
Cycle 2 Day 29	Predose ^a	00:00	X	*	X	
Cycle 3 Day 1	Predose ^a	00:00	X		X	
Cycle 3 Day 1	EOIb	EOIb	X			
Cycle 3 Day 1		04.00	X			
Cycle 3 Day 2		24:00	X			
Cycle 3 Day 3- Day 5		48:00-96:00	X			
Cycle 3 Day 8		168:00	X			
	•		•	·		

Protocol Amendment No.: 07

Predose: All predose samples should be taken within 30 minutes prior to the start of any treatments.

The EOI occurs when the entire BMS-986258 dose in the infusion bag is administered to the patient. If diluent is used to flush the dose remaining in the infusion line, then the EOI will occur when there is no dose is remaining in the infusion line after a flush. A PK sample should be taken immediately prior to the EOI (preferably within 2 minutes prior to the EOI). If the EOI is delayed to beyond the nominal infusion duration (30 minutes), the collection of this sample should also be delayed accordingly. EOI samples may not be collected from the same IV access as the drug was administered.

Table 9.5-4: Pharmacokinetic and Immunogenicity Sampling Schedule for BMS-986258 Q4W in Combination with Nivolumab Q4W in Dose Escalation (Part B)

Study Day of Sample Collection (1 Cycle = 8 Weeks)	Event	Time (Relative To BMS-986258 Dose) Hour:Min	PK Serum Samples for BMS-986258	ADA Samples for BMS- 986258	
Cycle 3 Day 15		336:00	X		
Cycle 3 Day 22		504:00	X		
Cycle 3 Day 29	Predose ^a	00:00	X	X	
Cycle 5 and every other cycle (i.e., cycle 7, 9,) Day	Predose ^a	00:00	X	X	
EOT			X	X	
30 day follow up			X	X	
60 day follow up			X	X	
100 day follow up			X	X	

Abbreviations: ADA, anti-drug antibody; EOI, end of infusion; EOT, end of treatment; PK, pharmacokinetics.

Protocol Amendment No.: 07

930120074 9.0

Approved v2.0

^a Predose: All predose samples should be taken within 30 minutes prior to the start of any treatments.

b The EOI occurs when the entire BMS-986258 dose in the infusion bag is administered to the patient. If diluent is used to flush the dose remaining in the infusion line, then the EOI will occur when there is no dose is remaining in the infusion line after a flush. A PK sample should be taken immediately prior to the EOI (preferably within 2 minutes prior to the EOI). If the EOI is delayed to beyond the nominal infusion duration (30 minutes), the collection of this sample should also be delayed accordingly. EOI samples may not be collected from the same IV access as the drug was administered.

Table 9.5-5: Pharmacokinetic and Immunogenicity Sampling Schedule for BMS-986258 Q4W in Combination with Nivolumab Q4W in Dose Expansion (Part C)

Study Day of Sample Collection (1 Cycle = 8 Weeks)	Event	Time (Relative To BMS-986258 Dose) Hour:Min	PK Serum Samples for BMS-986258	ADA Samples for BMS- 986258	
Cycle 1 Day 1	Predose ^a	00:00	X	X	
Cycle 1 Day 1	EOI ^b	EOI ^b	X		
Cycle 1 Day 29	Predose ^a	00:00	X	X	
Cycle 1 Day 29	EOI ^b	EOI ^b	X		
Cycle 2 Day 1	Predose ^a	00:00	X	X	
Cycle 2 Day 29	Predose ^a	00:00	X	X	
Cycle 3 Day 1	Predose ^a	00:00	X	X	
Cycle 3 Day 29	Predose ^a	00:00	X	X	
Cycle 5 and every other cycle (i.e., cycle 7, 9,) Day 1	Predose ^a	00:00	X	X	
EOT			X	X	
30 day follow up			X	X	
60 day follow up			X	X	
100 day follow up			X	X	

Abbreviations: ADA, anti-drug antibody; EOI, end of infusion; EOT, end of treatment; PK, pharmacokinetics.

9.6 Pharmacodynamics

For details about biomarkers, please see Section 9.8.

9.7 Pharmacogenomics

Not applicable.

[figure not shown]
Protocol Amendment No.: 07

^a Predose: All predose samples should be taken within 30 minutes prior to the start of any treatments.

[figure not shown]
b The EOI occurs when the entire BMS-986258 dose in the infusion bag is administered to the patient. If diluent is used to flush the dose remaining in the infusion line, then the EOI will occur when there is no dose is remaining in the infusion line after a flush. A PK sample should be taken immediately prior to the EOI (preferably within 2 minutes prior to the EOI). If the EOI is delayed to beyond the nominal infusion duration (30 minutes), the collection of this sample should also be delayed accordingly. EOI samples may not be collected from the same IV access as the drug was administered.

[figure not shown]
9.7.1 ADME Sampling

[figure not shown]
Not applicable.

Protocol Amendment No.: 07

Date: 16-Jun-2021

[figure not shown]
118

Clinical Protocol
BMS-986258

CA031002
Anti-TIM-3 mAb

Protocol Amendment No.: 07

9.9 Health Economics OR Medical Resource Utilization and Health Economics

Health Economics/Medical Resource Utilization and Health Economics parameters will not be evaluated in this study.

10 STATISTICAL CONSIDERATIONS

10.1 Sample Size Determination

[figure not shown]
10.1.1 Dose Escalation

During the dose escalation phase, an adaptive dose escalation scheme (BLRM for monotherapy and BLRM-copula for combination therapy) employing the EWOC principle will be used. The method is fully adaptive, makes use of all the information available at the time of each dose assignment, not just data from the current dose level, and directly addresses the ethical need to control the probability of overdosing.

The operating characteristics of BLRM for monotherapy escalation and BLRM-copula for combination therapy escalation were studied in various scenarios through simulations in .

The maximum number of participants treated will be for dose escalation Part A (BMS-986258 monotherapy) and for Part B (BMS-986258 in combination with nivolumab).

Approximately participants will be treated at the starting dose levels of BMS-986258 or BMS-986258 in combination with nivolumab. While the BLRM/BLRM-copula will use DLT information from the DLT period only, clinical assessment will take into consideration the totality of available data including PK/PD from all treated participants encompassing monotherapy and combination therapy, in assigning a dose level for the next cohort of participants. At least DLT-evaluable participants will be treated at the MTD. At most DLT-evaluable participants will be treated at each dose level. Additional participants may be treated at or any dose level below the estimated MTD for further evaluation of safety, PK, or PD parameters as required for a total of up to across doses for monotherapy and for combination therapy.

The final recommended MTD/RP2D will be based on the recommendation from the BLRM/BLRM-copula and overall clinical assessment of all available safety, PK, PD and efficacy data. Lower doses of BMS-986258 may be tested if none of the planned doses are found to be tolerable as monotherapy or in combination with nivolumab. Such decisions will be made after discussion and agreement between the Investigators and the BMS Medical Monitor.

Sample size calculations for the SC study (Part A1) are based on width of the confidence interval for the geometric mean ratio (GMR) of exposure measures for SC and IV dosing. For each dose to be tested in Part A1, the PK parameters are assumed to be distributed log-normally,

To account for potential missing data, approximately subjects will be treated for each dose to be tested in Part A1.

In addition, up to participants will be enrolled in each of the Part A and B NSCLC PD cohorts

In addition, up to participants will be enrolled in each of the Part A and B NSCLC PD cohorts in monotherapy and combination, with the goal of obtaining at least participants with evaluable pairs of screening and on-treatment biopsies, in order to evaluate PD changes in NSCLC tumors with minimum.

For example, assuming a intra-participant standard deviation, about participants per dose level will be needed to estimate the change from baseline with the above precision; However, in order to account for non-evaluable biopsy samples or lack of repeat biopsy due to early dropouts, about more participants would be needed (eg, in order to have evaluable participants, up to will need to be treated per dose level).

Clinical Protocol

BMS-986258

CA031002

[figure not shown]
Anti-TIM-3 mAb

10.1.2 Cohort Expansion

The purpose of cohort expansion is to gather additional safety, tolerability, preliminary efficacy, PK, and PD information regarding BMS-986258 in combination with nivolumab. However, the sample size is strictly based on efficacy, specifically on the target ORR relative to historic response rate.

Part C will be an expansion phase for BMS-986258 in combination with nivolumab and may include participants with RCC, CRC, NSCLC, SCCHN, and TNBC. Enrolled participants with RCC, SCCHN, NSCLC and CRC MSI-H will be relapsed or refractory to prior PD-(L)1 treatment. Participants with a diagnosis of RCC, CRC, NSCLC, and SCCHN may be selected

Each disease cohort expansion will be handled independently and there will be no multiplicity adjustment. Up to participants may be treated per expansion cohort (for a total of in Part C overall) to allow for if needed per tumor cohort, although a total of up to participants need to be treated across tumor cohorts based on the sample size assumptions and characteristics in the 2-stage design shown below.

10.2 Populations for Analyses

For purposes of analysis, the following populations are defined in Table 10.2-1 below:

Table 10.2-1: Population for Analyses

Population	Description
Enrolled	All participants who sign informed consent and are registered into the IRT.
Treated	All participants who take at least 1 dose of study treatment.
Response-evaluable	All treated participants with measurable disease at baseline and one of the following: (a) at least 1 post-baseline tumor assessment, (b) clinical progression, (c) death.
Pharmacokinetic	All treated participants who have concentration-time data.
Immunogenicity	All treated participants who have baseline and at least 1 post baseline pre-infusion immunogenicity assessment.

Abbreviations: IRT, Interactive Response Technology.

10.3 Statistical Analyses

The Statistical Analysis Plan will be developed and finalized before database lock and will describe the selection of participants to be included in the analyses. Below is a summary of planned

Protocol Amendment No.: 07

statistical analyses. Results will be presented by study part; data for participants who cross over from the SC cohort (A1) to IV monotherapy or combination treatment will be tabulated separately.

10.3.1 Efficacy Analyses

The primary efficacy analyses (Table 10.3.1-1) will be performed on the treated population for the final analysis. Efficacy analyses based on the response-evaluable population may be performed for interim analyses when the minimum follow-up period is less than sufficient to warrant adequate interpretation of the result. Details of the censoring scheme on time-to-event endpoints such as DOR, PFS, and OS rate will be described in the Statistical Analysis Plan.

 Table 10.3.1-1:
 Efficacy - Statistical Analyses

Endpoint	Statistical Analysis Methods
ORR is defined as the proportion of population of interest whose BOR is either CR or PR per RECIST v1.1 BOR for a participant will be assessed per RECIST v1.1.	Estimate of ORR and corresponding 2-sided exact 95% CI by treatment for each tumor type.
Median DOR DOR for a participant with a BOR of CR or PR is defined as the time between the date of first response and the date of the first objectively documented tumor progression per RECIST v1.1 or death, whichever occurs first.	Median duration of response using the Kaplan-Meier method and corresponding 2-sided 95% CI by treatment for each tumor type.
PFS rate at 6, 9, and 12 months PFS for a participant is defined as the time from the first dosing date to the date of first objectively documented disease progression or death due to any cause, whichever occurs first.	Estimate by the Kaplan-Meier method and corresponding 95% CI will be derived for each tumor type.

Abbreviations: BOR, best overall response; CI, confidence interval; CR, complete response; DOR, duration of response; ORR, overall response rate; PFS, progression free survival; PR, partial response; RECIST, Response Evaluation Criteria In Solid Tumors.

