10.3.8 Interim Analyses

The expansion phase of this study employs a 2-stage design framework. Therefore, there will be an interim analysis planned when an adequate number of treated participants have available tumor data. Additional interim analyses may also be performed for administrative purposes or publications. No formal inferences requiring any adjustment to statistical significance level will be performed.

Protocol Amendment No.: 07 Date: 16-Jun-2021

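### The plan does not say whether the Part C response rate and its exact 95% interval account for the two-stage design; if the stage-1 rule is followed, the ordinary versions lose their guarantee

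*Combined protocol and SAP*

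**What the plan says.** Section 10.3.8 states: "The expansion phase of this study employs a 2-stage design framework". It continues: "Therefore, there will be an interim analysis planned when an adequate number of treated participants have available tumor data". Section 10.1.2 says of Part C that "the sample size is strictly based on efficacy, specifically on the target ORR relative to historic response rate", and it ties the number treated to a two-stage layout: "based on the sample size assumptions and characteristics in the 2-stage design shown below". That layout (stage sizes, bounds, reference and target rates, error rates) cannot be read in the public document. Section 10.1.2 adds: "Each disease cohort expansion will be handled independently and there will be no multiplicity adjustment".

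On the analysis, Section 10.3.1 says: "The primary efficacy analyses (Table 10.3.1-1) will be performed on the treated population for the final analysis". The ORR row of Table 10.3.1-1 reads: "Estimate of ORR and corresponding 2-sided exact 95% CI by treatment for each tumor type". The row is shared by all study parts, and the readable text describes no response-based stages for Parts A and B. Section 10.3.8 also says: "No formal inferences requiring any adjustment to statistical significance level will be performed".

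Section 10.3 presents itself as a summary and leaves detail to a Statistical Analysis Plan due before database lock. For efficacy, the detail that Section 10.3.1 names as deferred is the censoring of time-to-event endpoints; the ORR method is not mentioned there. Section 4 lists ORR as a secondary endpoint for preliminary activity.

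**The concern.** The ordinary exact (Clopper-Pearson) interval limits each tail to 2.5% because the sample size is fixed in advance. Under a two-stage rule the final size is n1 or n1 + n2 according to the stage-1 responses. A cohort stopped for few responses keeps a low proportion that never gets the chance to recover. A cohort stopped early for many responses keeps a high one. The raw proportion is then biased and the per-tail guarantee is lost.

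At stake is how each tumor cohort is read against its historical rate, the comparison on which Part C is sized. After a futility stop, the upper limit would exclude the true ORR more often than its label says. Where early stopping for efficacy is allowed, the lower limit can fail in the same way.

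**Working it through.** **Inputs.** From the protocol: two stages with a look at tumor data (10.1.2, 10.3.8), and a two-sided exact 95% interval, that is 2.5% per tail (Table 10.3.1-1). Stage sizes, bounds and whether the rule is binding are not readable, so there is no stated figure to reproduce. The designs below are assumptions. In each, a cohort stops after n1 participants if responses are at or below the low bound (or at or above the high bound, where there is one), and otherwise adds n2.

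**Control without stopping.** For fixed n = 35, the ordinary interval has at most 2.49% in each tail and zero bias. Any excess below therefore comes from the stopping rule.

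**Method.** For true ORR p, each outcome that stops with x responses has probability C(n1, x) p^x (1−p)^(n1−x). Each outcome that continues to a total of s has the sum, over permitted stage-1 counts x, of C(n1, x) C(n2, s−x) p^s (1−p)^(n1+n2−s). The tail errors are P(lower limit > p) and P(upper limit < p), and the bias is E(raw ORR) − p.

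**One case by hand:** n1 = 10, stop at 0 responses, n2 = 19, p = 0.32.
- Stop at 0/10: probability 0.68^10 = 0.0211. The ordinary upper limit is 1 − 0.025^(1/10) = 30.8%, below 32%, so this outcome excludes the truth.
- Continue with totals 1 to 4 of 29: probabilities 0.0001, 0.0007, 0.0039 and 0.0135, together 0.0182. The ordinary upper limit for 4/29 is 31.7%, so these also exclude 32%. For 5/29 it is 35.8%, which does not.
- Upper-tail error: 0.0211 + 0.0182 = 0.0393, or 3.9% against 2.5%.
- Bias: E(ORR) = [10p + 19p(1 − (1−p)^10)]/29, so bias = −(19/29) p (1−p)^10. This is largest in size at p = 1/11: −(0.6552)(0.0909)(0.3855) = −0.0230, or −2.3 points.
- Stage-wise ordering ranks all low stops below all completed totals. The upper limit for total s solves P(stop at 0/10) + P(continue, total ≤ s) = 0.025. At p = 0.32 the left side is 0.0219 for s = 2 and 0.0258 for s = 3. Only 0/10 and totals 1 and 2 exclude 32%, so the error is 2.2%.

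**Eight assumed designs**, true ORR 2% to 44.5% in steps of 0.25 points, ordinary interval and raw ORR:

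| n1 | stop low at ≤ | stop high at ≥ | n2 | worst lower-limit tail | worst upper-limit tail | minimum coverage | extreme bias (points) |
|---|---|---|---|---|---|---|---|
| 10 | 0 | none | 19 | 2.49% | 4.13% | 93.87% | −2.30 |
| 12 | 0 | none | 18 | 2.47% | 4.14% | 94.34% | −1.77 |
| 15 | 1 | none | 20 | 2.44% | 3.68% | 94.00% | −1.93 |
| 18 | 2 | none | 20 | 2.48% | 3.97% | 94.25% | −1.80 |
| 12 | 0 | 3 | 18 | 3.37% | 4.05% | 93.86% | −1.37, +2.44 |
| 15 | 1 | 5 | 20 | 3.50% | 3.61% | 94.17% | −1.65, +2.42 |
| 20 | 2 | 6 | 20 | 3.21% | 3.50% | 94.86% | −1.23, +1.65 |
| 20 | 1 | 4 | 15 | 2.75% | 3.27% | 94.50% | −0.72, +1.07 |

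With stage-wise ordering, both tails are at most 2.5% and coverage is at least 95.1% in all eight. The uniformly minimum-variance unbiased estimate (UMVUE) has zero bias.

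**Wider scan**, 400 designs (n1 10 to 20, n2 10 to 25, low bound 0 to 3, with or without a high bound). The worst tail exceeds 2.5% in every one. It is 3.0% to 4.3% for the 80 futility-only designs (always the upper limit falling too low) and 2.7% to 4.3% for the 320 with both bounds (either tail). Bias reaches −4.4 points for futility-only designs and runs from −4.3 to +4.5 points for designs with both bounds.

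**The case against.** The readable text gives no stopping rule, does not say that one is binding, and does not say whether it covers futility only or efficacy too. If every cohort completes whatever its stage-1 result, the ordinary interval is valid and the bias is zero. A stage-wise interval is also an exact interval, so Table 10.3.1-1 does not exclude one. The reference list contains two papers on multistage phase II designs, but the text citing them is not readable, and a SAP is still to come. All of this stands. A reader might infer that the plan disregards the stages, or that the Section 10.3.8 sentence on significance levels is a decision to leave the interval unadjusted. The documents support neither. They show only that no method is named.

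The numerical case for a small effect is also fair. In the eight designs, mean coverage is 97.3% to 97.7%. Coverage drops below 95% at only about 1% to 8% of the true ORRs scanned, and for ORR up to 25% it is at least 95.2% throughout. In the four futility-only designs no tail exceeds 2.5% for ORR up to 20%. Low rates are plausible here: Section 3.3 cites an ORR of 4.7% for a comparable combination, and most Part C cohorts must be resistant to anti-PD-(L)1 therapy.

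Two things remain. With early efficacy stopping, a single tail still reaches 3.5% at low ORR. And the futility bias is largest at low ORR: in the case worked by hand it peaks at a true ORR of 9.1%, where 2.3 points is about a quarter of the rate (0.0230/0.0909 = 0.25).

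**Conclusion.** The point holds in conditional form. Part C has two stages and is sized on ORR, and the readable plan names no estimator or interval that uses the stages. If the stage-1 rule is followed and the ordinary methods are used, the 2.5% per-tail guarantee is lost and the raw ORR is biased.

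The size rests entirely on assumed designs: a worst single tail of 3.3% to 4.1% in the eight listed and about 2.7% to 4.3% across the wider scan; minimum coverage of 93.9% to 94.9% in the eight, at isolated true ORRs; and bias within about 2.4 points in the eight. No single figure such as 3.9% belongs to this trial, and none should be taken as its upper bound. The direction of bias cannot be stated: it is downward if stopping is for futility only, and can go either way if efficacy stopping is allowed.

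A reader might go further and call the Part C intervals invalid. That is not supported, because the rule is unreadable and total coverage is mostly above 95%. The weight is low to moderate: ORR is secondary and preliminary, and the interval is not described as a decision rule.

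**What to change.** In Table 10.3.1-1 or the SAP, add a line for Part C cohorts run under the two-stage rule: report the exact 95% interval from stage-wise ordering of the two-stage outcomes (Jennison-Turnbull type), and give the UMVUE or median-unbiased ORR beside the raw proportion. Keep the ordinary exact interval for Parts A and B and for any cohort that completes under a non-binding rule. State in advance whether the stage-1 rule is binding and whether it allows stopping for efficacy. If the sponsor prefers the ordinary interval throughout, the plan should label it descriptive and unadjusted for the stages.

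The cost is a few lines of wording and code. The downside is two ORR figures per Part C cohort and intervals that are sometimes slightly wider or shifted. In the case worked by hand, the upper limit for 4/29 moves from 31.7% to 34.3%, the p at which P(stop at 0/10) + P(continue, total ≤ 4) = 0.025.
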